### **8.5 Patient Compliance**

The study nurse will monitor eDiary compliance by routine review of the CRF health website. If both diary entries on a day are missing, the study nurse will call the patient/caregiver to remind them to complete all scheduled entries. Any noncompliance will be documented and explained in the source documents.

Study drug compliance will also be checked through diary responses. Additionally, patients will return all unused study drug at Visits 4, 5, 6, 7, 8, and 9. The study site staff will count all returned drug, assess compliance, and record details in the eCRF.

Treatment Compliance =  $100 \times ((\text{Number of study drug dispensed} - \text{number of study drug returned}) / \text{number of study drug that should be taken})$ .

Treatment compliance between 80% and 120% will be acceptable.

### **8.6 Study Drug Accountability**

Records shall be maintained of the delivery of study treatment(s) to the study site(s), of the inventory at the study site(s), of each use of the study treatment(s) for each patient, and of the return of unused study treatment(s) to Albireo.

These records shall include dates, quantities, batch numbers, expiry dates, and the unique code numbers assigned to the study drug and to the study patients.

The investigator will be responsible for ensuring that the records adequately document that the patients were provided the quantities specified in the protocol and that all study drug received from Albireo is reconciled.

### **8.7 Concomitant Therapy and Prohibited Medications**

The investigator will note all ongoing medication and any medication recently stopped (within 1 month prior to Visit 1) in the eCRF. At Visits 2 through 10, all changes in medication (stopping or starting new medication or changes in dose) will be recorded in the eCRF. All medications (prescribed or over the counter) for pruritus and sleep will be recorded.

All medications taken by a patient within 3 months prior to the first intake of study drug are regarded as prior medication.

All medications taken by a patient on or after the first intake of study drug, and which continue to be taken during the study, are regarded as concomitant medication.

Prohibited medications are listed in [Appendix 1](#).

## 9 ASSESSMENT OF EFFICACY

### 9.1 Efficacy Endpoints

#### 9.1.1 Primary Efficacy Endpoint

The primary efficacy endpoints are as follows:

- **European Union (EU) and rest of the world (RoW):** Proportion of patients experiencing at least a 70% reduction in fasting s-BA concentration from baseline to the end of treatment or reaching a level  $\leq 70$   $\mu\text{mol/L}$  compared to placebo after 24 weeks of treatment.

Fasting s-BA baseline will be calculated as the average of the value at randomization and the previous visit (Clinic Visit 2). The end value is the average of the values at Weeks 22 and 24 after the start of double-blind treatment.

- **United States (US):** Proportion of positive pruritus assessments at the subject level over the 24-week Treatment Period. A positive pruritus assessment is defined as a scratching score of  $\leq 1$  or at least a one-point drop from baseline on the Albireo ObsRO instrument. At each assessment, the AM score will be compared to the AM baseline, and the PM score will be compared to the PM baseline. Both AM baseline and PM baseline pruritus assessments will be included in the analysis of this endpoint. AM scores from the 14 days prior to the first dose of study medications will be averaged as AM baseline. PM scores from the 14 days prior to the first dose will be averaged as PM baseline.

#### 9.1.2 Secondary Efficacy Endpoint

Secondary efficacy endpoints include the following:

- **EU and RoW:** Proportion of positive pruritus assessments at the subject level over the 24-week Treatment Period. A positive pruritus assessment is defined as a scratching score of  $\leq 1$  or at least a one-point drop from baseline on the Albireo ObsRO instrument. At each assessment, the AM score will be compared to the AM baseline, and the PM score will be compared to the PM baseline. Both AM baseline and PM baseline pruritus assessments will be included in the analysis of this endpoint. AM scores from the 14 days prior to the first dose of study medications will be averaged as AM baseline. PM scores from the 14 days prior to the first dose will be averaged as PM baseline.
- **US:** Proportion of patients experiencing at least a 70% reduction in fasting s-BA concentration from baseline to the end of treatment or reaching a level  $\leq 70$   $\mu\text{mol/L}$  compared to placebo after 24 weeks of treatment.
- **All Regions:**

All secondary endpoints are compared to placebo.

- Change from baseline to Week 12 and to Week 24 in fasting serum bile acids
- Change from baseline to Week 12 and to Week 24 in serum ALT concentration
- Change in growth from baseline to Week 12 and to Week 24
- Proportion of responders for pruritus scores at Weeks 12 and 24 based on the Albireo PRO and ObsRO instruments
- Change in sleep parameters measured with the Albireo PRO and ObsRO instruments from baseline over the 24-week Treatment Period
- Proportion of individual assessments meeting the definition of a positive pruritus assessment at the subject level over the 24-week Treatment Period. A positive pruritus assessment includes an itch score  $\leq 1$ , or at least a one-point drop from baseline based on the Albireo PRO instrument; only patients  $\geq 8$  years of age will complete the Albireo PRO instrument
- Proportion of individual assessments meeting the definition of a positive pruritus assessment at the subject level from Weeks 0-4, Weeks 0-8, Weeks 0-12, Weeks 0-18, Weeks 0-24, respectively, or the proportion of positive pruritus assessments at each 4-week interval.
- Proportion of individual AM assessments meeting the definition of a positive pruritus assessment at the subject level from Weeks 0-4, Weeks 0-8, Weeks 0-12, Weeks 0-18, Weeks 0-24, respectively, or the proportion of positive pruritus assessments at each 4-week interval.
- Proportion of individual PM assessments meeting the definition of a positive pruritus assessment at the subject level from Weeks 0-4, Weeks 0-8, Weeks 0-12, Weeks 0-18, Weeks 0-24, respectively, or the proportion of positive pruritus assessments at each 4-week interval.
- Number of patients undergoing biliary diversion surgery or liver transplantation

### 9.1.3 Exploratory Efficacy Endpoints

Exploratory efficacy endpoints are compared to placebo and include the following:

- Assessment of Global Symptom Relief at Weeks 4, 12, and 24 as measured by patient, caregiver, and clinician via the PGIC items ([Appendix 3](#))
- Change from baseline in fasting s-BA at Week 4

- Change in pruritus, as indexed by caregiver-reported observed scratching, from baseline by each 4 week-interval of the Treatment Period as measured by the Albireo ObsRO instrument
- Change from baseline by each 4-week interval of the Treatment Period in patient-reported and observer-reported night time itching and scratching severity scores, respectively
- Change from baseline by each 4-week interval of the Treatment Period in patient-reported and observer-reported morning time itching and scratching severity scores, respectively
- Change from baseline by each 4-week interval of the Treatment Period in pooled pruritus score including observer-reported scratching for patients <8 years of age and patient-reported itch severity for patients  $\geq 8$  years of age
- Change from baseline by each 4-week interval of the Treatment Period in additional patient-reported and observer-reported sleep parameters (e.g., tiredness and number of awakenings)
- Change from baseline to Week 24 in PedsQL ([Appendix 4](#))
- Change from baseline in serum ALT concentration at Week 4
- Change from baseline in total bilirubin at Weeks 4, 12, and 24
- Change from baseline in AST and GGT at Weeks 4, 12, and 24
- Change from baseline for other biochemical markers and measures of bile acid synthesis (autotaxin, p-C4) at Week 24
- Change in pediatric end-stage liver disease/model for end-stage liver disease (PELD/MELD) score, AST to platelet ratio index (APRI) score, and Fib-4 score from baseline to Week 24
- Change from baseline to Week 24 in stage of liver fibrosis as assessed by Fibroscan® (where available)
- Liver-related mortality and liver decompensation events
- All-cause mortality

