#### 9.2.7 Fibroscan®

Where available, Fibroscan® will be performed as per institution standard practice at Visits 3 and 9.

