## 2 STUDY SYNOPSIS

Name of Sponsor/Company: Albireo	Name of Product: A4250	Name of Active Ingredient: A4250
Title of Study: A Double-Blind, Randomized, Placebo-Controlled, Phase 3 Study to Demonstrate Efficacy and Safety of A4250 in Children with Progressive Familial Intrahepatic Cholestasis Types 1 and 2 (PEDFIC 1)		
Principal Investigator: [REDACTED]		
Study Centers: Up to 50 sites will be initiated for this study in the United States (US), Canada, European Union (EU), Middle East, and Australia.		
Publication(s): None.		
Planned Study Period: Q2 2018 to Q4 2019	Development Phase: Phase 3	
Objectives: Primary Objectives To demonstrate the efficacy of repeated daily doses of 40 µg/kg/day and 120 µg/kg/day A4250 in children with progressive familial intrahepatic cholestasis (PFIC) Types 1 and 2, as determined by the following: 
 
• Proportion of patients experiencing at least a 70% reduction in fasting serum bile acid (s-BA) concentration from baseline to end of treatment or reaching a level ≤70 µmol/L compared to placebo after 24 weeks of treatment
 
• The proportion of positive pruritus assessments at the subject level over the 24-week Treatment Period
 
 Secondary Objectives 
 
• To evaluate the effect of A4250 on serum alanine aminotransferase (ALT) concentration
 
• To evaluate the effect of A4250 on growth
 
• To evaluate the effect of A4250 on sleep disturbance
 
• To evaluate the effect of A4250 on the need for surgical treatment (biliary diversion or liver transplantation)
 
• To assess the safety and tolerability of repeated daily doses of A4250 for 24 weeks
 
		

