#### 9.2.7 Fibroscan®

Where available, Fibroscan® will be performed as per institution standard practice at Visits 3 and 9.

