placebo and high dose vs. placebo will be calculated, respectively. If both individual p-values are  $\leq 0.025$ , a significant treatment effect will be declared on both dose groups. If only one of them is  $\leq 0.025$ , a significant treatment effect will be declared on the corresponding dose group.

Other secondary and exploratory outcome variables will provide supportive efficacy and safety information regarding the differences between the treatment groups. No adjustments will be performed for multiple comparisons when testing secondary and exploratory efficacy variables.

If not otherwise specified, the baseline value of a parameter is defined as the last assessment of that parameter prior to the first intake of study treatment.

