#### **11.2.2.6 Evaluation of Secondary and Exploratory Efficacy Variables**

The change in the secondary endpoints such as serum bile acids, total bilirubin, ALT, growth, Albireo PRO and ObsRO sleep parameters, and patient-reported itch severity will be

summarized by visit using descriptive statistics. Change in growth (weight for age and BMI for age) will also be displayed using graphical presentations.

Proportion of responders at Weeks 12 and 24 based on the PRO/ObsRO instruments estimated from both distribution and anchor-based approaches will be analyzed using the same model as specified for the primary analysis for EU and RoW.

Proportion of individual assessments meeting the definition of a positive pruritus assessment at the subject level from Weeks 0-4, Weeks 0-8, Weeks 0-12, Weeks 0-18, Weeks 0-24, respectively, or the proportion of positive pruritus assessments at each 4-week interval over the 24-week treatment period for AM or PM, respectively will be analyzed using the same model as specified for the primary analysis for US.

Undergoing biliary diversion surgery and/or liver transplant, all-cause mortality, and liver decompensation events will mainly be analyzed by using descriptive statistics. Kaplan-Meier curves will be used when appropriate for time to event data.

Comparisons of the change from baseline at Week 24 in PedsQL between the treatment groups will be conducted using ANCOVA. The model will include terms for baseline, PFIC class, age class, and treatment.

Other exploratory variables (Global Symptom Relief, biochemical markers and measures of bile acid synthesis, additional Albireo PRO and ObsRO sleep parameters, PELD/MELD score, APRI score, and Fib-4 score) will be analyzed descriptively for categorical and continuous data, as applicable. For continuous data, the change from baseline will be analyzed in addition to the actual visit values. For categorical data, shift tables or frequency and percentages of patients will be presented as appropriate. Additional details on secondary and exploratory efficacy variables and subgroup analyses by age class (6 months to 5 years, 6 to 12 years, and 13 to  $\leq 18$  years) will be specified in the SAP.

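### The exploratory Fibroscan endpoint is defined as a change in fibrosis stage, which gives up information that the stiffness reading from the same scans would keep

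*Protocol*

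**What the plan says.** The same text stands in the protocol versions of 24 June 2019 and 29 April 2019.

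- **Endpoint (Section 9.1.3):** "Change from baseline to Week 24 in stage of liver fibrosis as assessed by Fibroscan", limited to sites that have the device. The list opens with "Exploratory efficacy endpoints are compared to placebo and include the following", so stage is meant to be set against placebo.
- **Measurement (Section 9.2.7):** the scan "will be performed as per institution standard practice at Visits 3 and 9". No stage scale, cut-offs, central reading or person assigning the stage is named, and the recorded value is not specified.
- **Sites (Synopsis):** "Up to 50 sites will be initiated for this study".
- **Analysis (Section 11.2.2.6):** Fibroscan is not named among the other exploratory variables. Those are handled descriptively, with shift tables or frequencies for categorical data. "Additional details on secondary and exploratory efficacy variables and subgroup analyses by age class" are left to the SAP, which is not at hand.
- **Multiplicity (Section 11.2.2.1):** "No adjustments will be performed for multiple comparisons when testing secondary and exploratory efficacy variables".
- **Other fibrosis markers (Section 9.2.8):** APRI and Fib-4 are given by formula and are numeric scores.

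**The concern.** The protocol fixes the outcome variable itself as a class. An SAP written to this protocol could add cut-offs to the stage, but it could not restore the underlying reading unless that reading is captured at the visits, and the text does not say that it is. A child whose stiffness falls without crossing a cut-off counts as unchanged, while a child close to a cut-off can change stage on a trivial difference.

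Numbers are small. The plan has 20 children per arm (Section 7.1.1), and only those at sites with the device contribute. Fibroscan is the only imaging measure of fibrosis stage, and the only fibrosis marker set as a class. If the reading is not recorded during the trial, it may not be recoverable afterwards.

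A second, weaker issue is that scanning follows local practice and no common scale is named. Nothing in the text therefore ensures that a one-stage change means the same thing at every site.

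**Working it through.** **No stated figure.** The protocol gives no effect size, SD or power for Fibroscan, so there is nothing to reproduce. The inputs below are assumptions, varied over a range.

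**Measure of loss.** Relative efficiency of change in stage against change in the continuous value:

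E = (Δ_stage² / σ²_stage) / (Δ_cont² / σ²_cont)

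Here Δ is the difference between arms in mean change and σ² is the variance of change. E is the ratio of effective sample sizes, and the loss is 1 − E.

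**Inputs.** Normal latent scale; correlation r between baseline and Week 24 of 0.5, 0.7 or 0.9; treatment shift of 0.3 or 0.5 SD (0.4 for uneven stages); 1,000,000 simulated children per arm; common cut-offs.

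| Stages (share of children, lowest to highest) | E, r = 0.5 | E, r = 0.7 | E, r = 0.9 |
|---|---|---|---|
| 5, even | 0.78–0.80 | 0.72–0.74 | 0.54–0.58 |
| 5, uneven 5/15/20/20/40% | 0.81 | 0.74 | 0.55 |
| 5, uneven 3/7/10/20/60% | 0.70 | 0.62 | 0.45 |
| 5, uneven 50/20/15/10/5% | 0.56 | 0.50 | 0.37 |
| 3, even | 0.64–0.66 | 0.54–0.57 | 0.34–0.37 |
| 2, even | 0.45–0.47 | 0.35–0.37 | 0.18–0.21 |

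**Five even stages.** The loss runs from 1 − 0.80 = 20% to 1 − 0.54 = 46%. Even if all 20 children per arm were scanned, analysing stage would be worth 20 × 0.54 = 10.8 to 20 × 0.80 = 16 children analysed on the reading. If both analyses are adjusted for baseline, five even stages keep 0.58 to 0.84.

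**More than half lost.** This happens with two stages at every r tried, with three stages at r = 0.9, and with two of the three uneven five-stage distributions at r = 0.9.

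**Cut-offs that differ between sites.** Shifting cut-offs between sites with an SD of 0.5, the same shift applying at both of a child's visits, lowers E by a further 0.01 to 0.06. Five even stages then keep 0.49 to 0.75. The added loss is small because the endpoint is a change within one child.

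**Illustration in power.** Assume 15 children per arm, baseline log-stiffness SD 0.5, a true log reduction of 0.25 (1 − e^−0.25 ≈ 22%) and a two-sided 5% t test.

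| SD of change | Continuous | 5 even | 4 even | 4 uneven (60/20/10/10%) |
|---|---|---|---|---|
| 0.2 | 91% | 63% | 55% | 35% |
| 0.3 | 59% | 38% | 34% | 23% |

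These settings are unfavourable to staging. With equal variances, SD² of change = 2 × 0.5² × (1 − r). So 0.04 = 0.5 × (1 − r) gives r = 0.92, and 0.09 = 0.5 × (1 − r) gives r = 0.82. The first row also assumes an effect of 0.25/0.2 = 1.25 SD, which is large.

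**The case against.** The case on the other side has real weight.

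- **Cut-offs belong in the SAP.** Section 11.2.2.6 leaves further detail on exploratory variables to the SAP. This stands: missing cut-offs alone are not an error. It does not answer the choice of stage as the variable.
- **A reader might infer that staging throws away most of the measurement.** The documents do not support that. It depends on the number of stages, their distribution and the correlation, none of which is given. With five even stages, 54% to 80% of the information is kept.
- **A reader might infer that stages will not be comparable across sites.** That also goes too far. Section 9.2.7 ties institution practice to performing the scan and does not say that sites assign stages by their own thresholds. If readings are captured, common cut-offs can be applied later. What remains is that comparability is not ensured.
- **No test of stage is specified.** Fibroscan is not named in Section 11.2.2.6, and a shift table is already the stated treatment of categorical exploratory data. The only contrary text is the general line about comparison with placebo. The power figures therefore illustrate a loss and are not this trial's loss.
- **Fibrosis does not rest on Fibroscan alone.** APRI and Fib-4 are numeric and not limited by device availability, and ultrasound records echogenicity, nodules and spleen size (Section 10.2.7). This lowers the stakes.
- **The reading may already be recorded.** The eCRF is not shown. If so, the change is one of wording only.

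**Conclusion.** The point holds as a low-severity improvement. The endpoint is fixed as a class where the same scan yields a continuous value, and staging lost information in every setting tried: about 20% to 46% of effective sample size with five evenly filled stages, and over half with two stages, or with three or some uneven distributions at very high correlation. Comparability of stage across sites is not ensured, but the within-patient change keeps the added loss small (0.01 to 0.06 in relative efficiency).

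This rests on a normal latent scale, on assumed numbers and distributions of stages, on assumed correlations of 0.5 to 0.9, and on the general fact that the device returns a continuous stiffness reading. The endpoint is exploratory, unadjusted and collected only where available. Neither the primary claims nor the sample size depends on it.

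**What to change.** - In the Synopsis and Section 9.1.3, define the endpoint as change from baseline to Week 24 in liver stiffness (kPa, analysed on the log scale).
- In Section 9.2.7, require the reading to be recorded at Visits 3 and 9.
- In Section 11.2.2.6, compare log change with placebo by ANCOVA with treatment, baseline, PFIC class and age class, the model already given there for PedsQL.
- Keep stage, if wanted, only as a descriptive shift table, with one common set of cut-offs applied to the recorded readings.

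The cost is endpoint wording and, if the reading is not already captured, one eCRF field. The scans and visits stay the same.

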## 9.2 Efficacy Assessments

### 9.2.1 Serum Bile Acids

Blood samples for analysis of fasting total s-BA will be drawn at all visits. Patients will fast (water intake only is permissible) for at least 4 hours prior to the collection of samples for s-BA. Exceptions can be made for infants, <12 months of age, if unable to fast for the full 4 hours. Any visit at which a bile acid sample result is unreportable, an additional unscheduled visit for a repeat sample collection may be scheduled. All s-BA results during

the treatment period and follow-up will be blinded. Samples will be processed and transported to a central laboratory per instructions in the laboratory manual.

### **9.2.2 Itching, Scratching and Sleep Score**

Itching, observed scratching, and sleep disturbance will be recorded twice each day via eDiary. Patients and/or caregivers will be instructed to complete the eDiary every day in the morning after the patient wakes and in the evening just before the patient goes to sleep throughout the study. Patients and caregivers will receive a formal training session during Visit 1.

The eDiary includes Albireo ObsRO and PRO items. Patients <8 years of age will not be asked to complete the Albireo PRO items; only the Albireo ObsRO will be completed by caregivers of patients in this age group. Older patients, 8 to 18 years of age, will complete the Albireo PRO items and the caregiver will complete the Albireo ObsRO items. The Albireo PRO items assess severity of itch, aspects of sleep disturbance (morning diary only), and tiredness. For patients 8 to 12 years of age, the caregiver will read the Albireo PRO items along with the child and record the child's response. A guide will be provided to the caregivers that provides standardized explanations of the Albireo PRO items, in case the patient is confused or requires clarification about the meaning of a question. The Albireo ObsRO items assess severity of observed scratching, aspects of observed sleep disturbance (morning diary only), and observed signs of tiredness (evening diary only). The Albireo ObsRO and PRO scratching and itch severity items use 0 to 4 response scales, where each response is distinguished by a unique facial expression, verbal anchor, number, and color code ([Appendix 2](#)). To meet eligibility criteria, a scratch score will be calculated from daily diary entries (ObsRO items) the 14 consecutive days prior to randomization.

A daily AM & PM score for the Albireo ObsRO scratching item will be averaged from the 2 ratings for each day. A daily score will be considered missing if both of the daily assessments are missing. A weekly score will be calculated by averaging the daily scratching scores. A weekly score will be considered missing if  $\geq 4$  out of 7 days a week of data are missing. For AM & PM baseline, a 14-day daily score of AM & PM prior to the first dose of study medications will be averaged as the baseline score.

For AM baseline, a 14-day AM score prior to the first dose of study medications will be averaged as the AM baseline score. The same approach will be used for PM baseline and to calculate a patient-reported itch severity score. The handling of missing data is described in [Section 11.2.2.2](#).

